## 1.0 Objectives

### 1.1 Study Objectives

To evaluate the efficacy of preoperative treatment with a novel, wireless, low-level microcurrent-generating antimicrobial device (brand name: JumpStart) in preventing the spread of *Propionibacterium acnes* in patients receiving open or arthroscopic shoulder surgery. Vomaris distributes Procellera™ AMT (advanced microcurrent technology) under the name Jumpstart™, exclusively through Arthrex, Inc. The FDA 510 documentation for Vomaris Procellera is attached in a separate document (as well as documentation regarding the distribution through Arthrex).

### 1.2 Primary Study Endpoints

The primary outcome measures the intraoperative culture results (e.g. positive vs negative, days to positive conversion) for *P. acnes* by evaluating bacterial cultures from punch skin biopsies at the time of the surgery. Any change in the condition of the biopsied area will be recorded and followed, including infections, as part of the routine care visits.

### 1.3 Secondary Study Endpoints

No secondary endpoints

## 2.0 Background

### 2.1 Scientific Background and Gaps

The spread of multi-drug resistant bacteria and financial burden of periprosthetic joint infection exacerbate the need for treatments to address pathogenic contamination and expedite healing. Although rare, these infections can place a great financial burden on the health care system and are often associated with increased hospital length of stay, compromised function, reduced quality of living, and increased likelihood of follow-up surgeries. Bacterial infection can further compound this problem with the widespread, prolonged use of prolonged antimicrobial prophylaxis. It is known that there is a high frequency of infections after open and arthroscopic shoulder surgery caused by *Propionibacterium acnes*. Because *P. acnes* normally colonizes under the epidermal layer in sebaceous glands, topical skin preparations, skin cleansers, and antibiotics may be unable to completely penetrate the deep layers of the skin to eradicate its colonization in all layers of the skin.

**Lee et al. (2014)** showed how *P. acnes*, which normally resides in the skin, can continue to persist in the skin despite standard surgical preparation. Ten healthy male subjects had received skin preparation of their upper back with ChloraPrep (2% chlorhexidine gluconate and 70% isopropyl alcohol) and two 3-mm dermal punch biopsy specimens were subsequently obtained. These dermal cultures were positive for *P. acnes* in 7 out of 10 subjects, where 4 subjects had *P. acnes* grow from 1 of 2 biopsies taken, whereas 3 subjects had it grow on 2 of 2 biopsies taken. This study showed how *P. acnes* persists in dermal tissue even with surface skin preparation that is considered standard in orthopedic surgery, at much higher rate than previously reported.

**Namdari et al. (2017)** studied the efficacy and safety of preoperative oral administration of doxycycline in decolonizing *P. acnes* from the skin over the shoulder in a randomized controlled trial. Patients, who were prospectively undergoing shoulder arthroscopy, were randomized in either the drug group (n=37) or standard of care (no drug) group (n=37), where the drug group administered oral doxycycline for 7 days before the surgery. Before the surgery, 2 separate 3-mm punch biopsy specimens were obtained from the sites of the anterior and posterior arthroscopic portals and were sent for culture in anaerobic and aerobic medium held for 13 days. Results showed that 22 patients in the no-drug group had at least 1 positive dermal culture, where 10 patients had 1 positive culture and 12 had 2 positive cultures. 16 patients in the drug group had at least 1 positive dermal culture, where 6 patients had 1 positive culture and 10 had 2 positive cultures. This data showed that the administration of oral doxycycline for 7 days before the did not reduce the colonization of *P. acnes* in a significant manner.

A novel, wireless, low-level microcurrent-generating antimicrobial device has been observed, *in vitro*, to exhibit electricidal effect in the presence of antibiotic and multidrug resistant clinical wound isolates. These energy-based systems were originally employed to augment wound healing process, reduce infection, and address edema and pain in the recent decades. Low-level microcurrents have been recently expanded into the orthopedic space as a bacterial growth inhibitor both *in vitro* and *in vivo*. Procellera (JumpStart) is a sterile single layer dressing consisting of a matrix of alternating silver (Ag) and zinc (Zn) dots that are held in positions on a polyester substrate with biocompatible binder. Dressing is then activated in the presence of a conductive fluid, which may come from wound exudate or exogenous fluids, such as saline.

Many studies have been done already on the wound healing and pain management properties of JumpStart, but only few have explored its bactericidal properties. Below is the summary of current literature related to this topic. The first study didn't look particularly at the antimicrobial effects, but rather the overall benefit of these microcurrent-generating dressings on patients who received knee replacements. The second study summarizes the *in vitro* antimicrobial properties of the dressings against various drug-resistant bacteria.

**Chow (2016)** performed a single-institution chart review to see the benefit of novel microcurrent-generating antimicrobial dressing (MCD) on patients who received total knee arthroplasty. The study was conducted on 92 patients who were all treated with MCD as a postoperative treatment from 2010 to 2013. MCD was applied using aseptic technique, directly on top of the adhesive skin closure strips, and was electrically activated and maintained moist by saturating with sterile hydrogel upon application. MCD was then covered with semi-occlusive dressing to secure it in place and to maintain a moist healing environment. Dressings were scheduled to be removed after a week post-procedure.

The results show that the use of MCD as an adjunct to standard surgical closure methods is safe and effective. The mean length of stay at the hospital was  $\sim$ 2.3 days, the mean length of treatment with MCD was  $\sim$ 8.3 days, and the mean follow-up time was 341 ( $\pm$  177 days). There was no infection observed, compared to 1.6% reported without MCD (found in literature), and the 30-day post-operative readmission rate was 2%, compared to 4% reported without MCD (found in literature). Knee Society Score function showed statistically significant improvements post-operatively, with a mean 6-month score of 75 ( $\pm$  20.3) and mean improvement of 36.3 ( $\pm$  21.1).

**Kim et al. (2014)** studied the *in vitro* efficacy of the antibacterial properties of bioelectric dressings containing silver and zinc against clinical wound isolates having unknown antibiotic resistance, including beta-lactamase (ESBL) bacteria, multidrug-resistant (MDR) bacteria, and methicillin-resistant *Staphylococcus aureus* (MRSA). Except for the *E. faecalis* isolates, all types of clinical bacterial isolates were killed completely within 24 hours of exposure to the bioelectric wound dressing, indicating the dressing has broad-spectrum bactericidal activity. For potential bacteriostatic *Enterococcus* isolates were also tested to determine how such isolates would react to longer incubation times of up to 48 hours. With the exception of *E. raffinosus* isolate, all the *Enterococcus* bacterial isolates had slightly decreased growth at 48 hours compared to with those exposed to the bioelectric wound dressing for 24 hours. The authors hypothesize that the Ag-Zn resistance in *Enterococcus* species may depend on the activation of endogenous silver and/or zinc efflux systems.

To date, no MRSA strains have been found to possess Ag-resistant genes, and there is no known mechanism of bacterial resistance to all heavy metal ions. However, studies have suggested that the widespread and uncontrolled use of Ag+ in wound care may result in more bacteria developing resistance.

## 2.2 Previous Data

No preliminary data.

## 2.3 Study Rationale

From current literature search, there is no study that evaluates the antimicrobial prophylaxis of microcurrent-generating antimicrobial dressings (e.g. JumpStart) for shoulder procedures in vivo.

# 3.0 Inclusion and Exclusion Criteria

## 3.1 Inclusion Criteria

- 18 years old or older
- Scheduled to receive open or arthroscopic shoulder surgery

## 3.2 Exclusion Criteria

- 17 years old or younger
- Pregnant women
- Prisoners
- Non-English speaking or unable to understand consent
- 
- History of previous shoulder infection or clinical signs of preoperative infection
- History of taking any antibiotic(s) within 4 weeks prior to the scheduled shoulder surgery
- History of allergy to zinc and silver
- No lesions, active acne or skin inflammatory disorders (psoriasis, eczema, etc.) in either shoulder

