# 4.0 Recruitment Methods

## 4.1 Identification of subjects

Patients will be identified in the Orthopedics Clinic for indications of open or arthroscopic shoulder surgery. Patients will be asked to join the study if they meet the selection criteria and agree to the plan of care with the microcurrent-generating antimicrobial dressing.

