#### 6.2.2 Explanation for why the research could not practicably be conducted without access to and use of PHI

The medical record will be reviewed during the clinic visit to determine eligibility.

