At the time of the surgery, 2 separate 3-mm punch biopsy specimens will be taken from the posterior shoulder skin of both shoulders using a disposable biopsy punch (Disposable Biopsy Punch; Robbins Instruments, Chatham, NJ, USA) (Figure 2) . The biopsy sites will be closed with an adhesive tape (Steri-Strip, 3M, Maplewood, MN, USA) and covered with a routine gauze dressing. Samples will be transferred directly into separate sterile specimen containers from the biopsy punches using clean, sterile forceps. Specimens will then be transferred directly to a single laboratory for culture. Anaerobic and aerobic culture substrates will be used and held for 14 days for *P. acnes* only, given literature that shows *P. acnes* can grow on either substrate. Anaerobic culture plates will be incubated for 4 days and broth cultures for 14 days before concluding that the final report is negative. To serve as a “negative control,” while wearing sterile gloves, in the first 20 patients, a sterile culture swab will be opened in the operating room, wiped through the air, and sealed in a specimen container. Chocolate plate will serve as a settle plate in the OR suite for 10 minutes and incubated for 4 days. Data will include demographic data of patients, positive culture rates, and the number of days before resulting in positive culture. All culture results will be reviewed and the patient will be marked positive if any of the cultures were positive. Patients will be scheduled for postoperative, routine follow-up visits. The rest of patient care will follow our current routine standard care without any modifications or interventions.

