### 7.4.3 Method for Assigning Subject to Treatment Groups

NA

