## 8.0 Subject Numbers and Statistical Plan

**8.1 Number of Subjects**

Thirty patients will be recruited for this study.

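### The skin-disease item in Section 3.2 is worded the wrong way round: as written it excludes patients with clear skin on both shoulders

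*Combined protocol and SAP*

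**What the plan says.** Section 3.2 (Exclusion Criteria) ends with the item "No lesions, active acne or skin inflammatory disorders (psoriasis, eczema, etc.) in either shoulder". A typical neighbour in the same list reads "History of previous shoulder infection or clinical signs of preoperative infection". Section 3.1 (Inclusion Criteria) has two entries, adult age and a scheduled shoulder operation, and says nothing about skin.

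The lists decide who enters. Section 4.1 states: "Patients will be asked to join the study if they meet the selection criteria". Section 6.2.2 adds: "The medical record will be reviewed during the clinic visit to determine eligibility".

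The skin that the item concerns is also the tissue that supplies the endpoint. Under Section 7.1, "2 separate 3-mm punch biopsy specimens will be taken from the posterior shoulder skin of both shoulders", and the primary outcome in Section 1.2 is obtained by "evaluating bacterial cultures from punch skin biopsies at the time of the surgery". Section 1.3 names no secondary endpoint.

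**The concern.** An exclusion list is read as: if the statement is true of the patient, the patient is out. Every other legible item in Section 3.2 works that way. The last one is phrased as a requirement for entry, so under its heading it does the opposite of what was surely meant.

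There are two possible consequences, and only one can apply to a given patient.

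- **Screened literally.** Patients with clear skin are refused and patients with skin disease are enrolled, including those with disease on one side only. The treated shoulder is always the operative one (Section 7.1), and Section 7.4.3 gives no assignment method, so side is not randomised. If skin condition affects culture positivity, a one-sided condition enters the within-patient comparison directly. Pairing removes what the two shoulders share, not what differs between them.
- **Screened by intent.** The results are unaffected, but each enrolled patient meets a written exclusion. Any eligibility record that follows the protocol's wording would then show a discrepancy. Section 20.1.1 opens the study documents to monitoring and audit.

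**Working it through.** The plan gives no figure on this point. The check compares the wording with its heading, looks for a correction elsewhere, and then counts.

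**1. Form of the items in Section 3.2.**

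- Bullets in the text as available: 9, of which 1 is blank.
- Legible items: 9 − 1 = 8.
- Items naming a disqualifying state: 7 (under age, pregnancy, imprisonment, language or inability to understand consent, infection, recent antibiotics, metal allergy).
- Items naming an absence: 8 − 7 = 1, the skin item.

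The blank bullet may come from how the text was extracted, and nothing is inferred from it.

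**2. What the item does under each heading.** Let *T* mean skin disease on the operative shoulder and *C* mean skin disease on the contralateral shoulder. The item asserts *not (T or C)*. Listed as an exclusion, it removes patients for whom *not (T or C)* is true. The evident intent is to remove patients for whom *(T or C)* is true.

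| Skin status | Item as written in 3.2 | Evident intent |
|---|---|---|
| Clear on both shoulders | excluded | eligible |
| Disease on operative side only | eligible | excluded |
| Disease on contralateral side only | eligible | excluded |
| Disease on both shoulders | eligible | excluded |

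The two readings disagree in all four rows, so no patient is classified the same way by both on this item.

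**3. Search for a correction elsewhere.**

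- Section 3.1 has no skin criterion.
- The infection item in Section 3.2 covers infection, not acne, psoriasis or eczema.
- Section 7.1 calls the contralateral shoulder normal, but that describes the control side and sets no entry rule.
- The consent form mentioned in Section 5.2.1 is not available to check.

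No legible text restates or corrects the item.

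**4. Counts.** Section 8.1 gives the number: "Thirty patients will be recruited for this study".

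- All screened by intent: 30/30 = 100% meet the exclusion as written.
- All screened literally: 0/30 have clear skin on both shoulders.
- Mixed screening: *k*/30 enrolled against the written text, with *k* anywhere from 0 to 30. The documents do not say which reading is used.
- Specimens taken from skin covered by the rule: 30 patients × 2 shoulders × 2 biopsies = 120, which is the whole planned set of biopsies.

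**5. Size of bias.** None can be calculated. It would need the frequency of one-sided skin disease among eligible patients and the *P. acnes* positivity rate by skin condition, and the documents report neither.

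**The case against.** The strongest reply is that nobody would apply the literal text. The study fixes an adhesive dressing to the skin and then biopsies it, and the adjacent items exclude infection and allergy. Surgeons present the study, and research staff see the patients in person. Refusing everyone with healthy skin would be absurd, and staff would notice. On that view this is an editorial note: the counts of 30/30 and 0/30 only restate the two readings, the bias argument depends on the unlikely one, and a screening form with correct wording may already exist.

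Much of this stands. Screening by intent is the likelier case, and the results are then untouched. The counts are logical consequences of the sentence, not measured effects. The bias route also needs a link between skin disease and culture results that the documents do not report: Section 2.1 describes where *P. acnes* normally lives but does not compare diseased with healthy skin. No screening form is in the documents, so a contradiction in the records is conditional on the form following the protocol. Section 6.2.2 justifies access to records and does not show that skin is judged from records alone.

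What does not stand is leaving the line as it is. The reply concedes that the wording is inverted. This is the only legible rule on these skin conditions, entry depends on the lists, and an eligibility list should not rely on staff reversing one of its lines.

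**Conclusion.** The point holds. The last item of Section 3.2 has the wrong polarity for its heading, and nothing legible elsewhere in the document corrects it. It is a wording error in an operative eligibility rule, not a questionable choice of design. It should be corrected, but it does not by itself threaten the analysis.

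The extent is all 30 patients under either uniform reading: all meet a written exclusion, or none has clear skin on both shoulders. No effect on the estimated difference between shoulders can be given. The conclusion assumes that the blank bullet and the consent form, neither of which can be checked, contain no correcting rule. The view that the results are probably unaffected assumes that staff screen by the evident intent.

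**What to change.** Make the wording agree with the heading in one of two equivalent ways:

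- delete the opening word *No* and keep the item in Section 3.2; or
- move the line unchanged to Section 3.1.

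In the notation above, the first excludes on *(T or C)* and the second requires *not (T or C)*; both give the evident-intent column of the table. Use only one of them, and use the same wording on any screening form that copies the criteria. If patients have already been enrolled, record which reading was applied.

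The cost is one deleted word or one moved line, plus the matching edit to any form. The sample size of 30, the McNemar comparison and the study procedures stay as they are.

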## 3.3 Early Withdrawal of Subjects

### 3.3.1 Criteria for removal from study

Patients will be removed from the study if reasons for safety or if the patient wishes to withdraw from the study.

### 3.3.2 Follow-up for withdrawn subjects

Patients withdrawn for any reason will be followed up as the standard of care protocol.

# 4.0 Recruitment Methods

## 4.1 Identification of subjects

Patients will be identified in the Orthopedics Clinic for indications of open or arthroscopic shoulder surgery. Patients will be asked to join the study if they meet the selection criteria and agree to the plan of care with the microcurrent-generating antimicrobial dressing.

## 4.2 Recruitment process

Patients will be recruited in the clinic for the study. The shoulder and elbow surgeons will provide the purpose and information of the study to the patient. An investigator will consent patients to the study if they wish to join.

## 4.3 Recruitment materials

NA

## 4.4 Eligibility/screening of subjects

Patients will be identified in clinic during their standard of care visit.

# 5.0 Consent Process and Documentation

## 5.1 Consent Process

### 5.1.1 Obtaining Informed Consent

#### 5.1.1.1 Timing and Location of Consent

Written consent will be obtained in the clinic with each patient

#### 5.1.1.2 Coercion or Undue Influence during Consent

An investigator will obtain consent for involvement in the study in the clinic. The investigator will express that this is an academic study and patient involvement is not necessary to their care. The patient has full right to choose to be involved with the study or to decline and it will not affect their care.

### 5.1.2 Waiver or alteration of the informed consent requirement

Waiver of informed consent is requested to review patients' medical records to identify potential subjects. There is no more than minimal risk to the privacy or welfare of included subjects in this retrospective research study. Data will be entered into study databases only. Only approved investigators may perform the retrospective data collection. No active research intervention is taking place.

## 5.2 Consent Documentation

### 5.2.1 Written Documentation of Consent

Written consent form is attached to this IRB submission

### 5.2.2 Waiver of Documentation of Consent (Implied consent, Verbal consent, etc.)

N/A

## 5.3 Consent – Other Considerations

### 5.3.1 Non-English Speaking Subjects

Patients who are non-English speakers will be excluded from this study.

### 5.3.2 Cognitively Impaired Adults

#### 5.3.2.1 Capability of Providing Consent

Patients not able to provide consent will be excluded. Whether the patient is able to provide informed consent will be decided by the PI.

#### 5.3.2.2 Adults Unable To Consent

N/A

#### 5.3.2.3 Assent of Adults Unable to Consent

N/A

### 5.3.3 Subjects who are not yet adults (infants, children, teenagers)

#### 5.3.3.1 Parental Permission

N/A

#### 5.3.3.2 Assent of subjects who are not yet adults

N/A

## 6.0 HIPAA Research Authorization and/or Waiver or Alteration of Authorization

### 6.1 Authorization and/or Waiver or Alteration of Authorization for the Uses and Disclosures of PHI

Check all that apply:

- Not applicable, no identifiable protected health information (PHI) is accessed, used or disclosed in this study. [Mark all parts of sections 6.2 and 6.3 as not applicable]
- Authorization will be obtained and documented as part of the consent process. [If this is the only box checked, mark sections 6.2 and 6.3 as not applicable]
- Partial waiver is requested for recruitment purposes only (Check this box if patients' medical records will be accessed to determine eligibility before consent/authorization has been obtained). [Complete all parts of sections 6.2 and 6.3]
- Full waiver is requested for entire research study (e.g., medical record review studies). [Complete all parts of sections 6.2 and 6.3]
- Alteration is requested to waive requirement for written documentation of authorization (verbal authorization will be obtained). [Complete all parts of sections 6.2 and 6.3]

### 6.2 Waiver or Alteration of Authorization for the Uses and Disclosures of PHI

#### 6.2.1 Access, use or disclosure of PHI representing no more than a minimal risk to the privacy of the individual

##### 6.2.1.1 Plan to protect PHI from improper use or disclosure

Information is included in the "Confidentiality, Privacy and Data Management" section of this protocol.

##### 6.2.1.2 Plan to destroy identifiers or a justification for retaining identifiers

Identifiers will be destroyed when the PI closes the study.

